2. STUDY PROCEDURES

a. Procedures

Patients from our endocrinology practice meeting our inclusion criteria will be consented into the study. They will be randomized into 1 of 2 treatment arms (Anastrozole 1 mg qday or Letrozole 2.5mg qday). Labs (gonadotropins, androgens, estrogens, growth factors, lipid profile) will be done every 6 months, bone age annually, and DEXA scans every 2 years.

We will see the patients annually until near final height (< 2 cm growth velocity per year), re-consenting in those over 18 years old. We will perform physical exams, obtain

anthropometric data, and repeat the above blood tests at least once off medication and perform imaging studies as warranted.

Beginning with this March 2016 renewal, we will no longer randomize to A vs L but use only A, continuing to collect observational data. **Procedure Risks**

We will be using the standard doses for the two drugs used. We will be monitoring with every 6 month physical exams and laboratory evaluation for possible side effects. At the discretion of the investigator, the medication may be reduced or discontinued, specifically if growth velocity falls below normal. **Use of Deception in the Study**

No deception will be used. Use of Audio and Video Recordings

No audio or video recording will occur. Alternative Procedures or Courses of Treatment

There are no alternatives to the above treatment. The only alternative would be to not start on the medication. Growth hormone is a theoretical option but is not standard of care for patients meeting these inclusion criteria. No standard treatment will be withheld. Will it be possible to continue the more (most) appropriate therapy for the participant(s) after the conclusion of the study?

Yes

g. Study Endpoint(s)

Our end point is final height which is defined as less than 2 cm of growth per year. We anticipate that all patients will reach this end point. **BACKGROUND**

a. Past Experimental and/or Clinical Findings

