5. DRUGS, BIOLOGICS, REAGENTS, OR CHEMICALS USED IN THE STUDY

a. Investigational Drugs, Biologics, Reagents, or Chemicals

Investigational Product 1		
Name:	NA	
Dosage:	NA	
Administration Route:	NA	

b. Commercial Drugs, Biologics, Reagents, or Chemicals

Commercial Product 1		
Name:	Letrozole (no longer being used)	
Dosage:	2.5 mg	
Administration Route	Oral	
New and different use? (Y/N)	Yes	
Commercial Product 2		
Name:	Anastrozole	
Dosage:	1 mg	
Administration Route	Oral	
New and different use? (Y/N)	Yes	

6. **PARTICIPANT POPULATION**

a. Planned Enrollment

120; boys with short stature and/or growth hormone deficiency which may be congenital or acquired (post surgical or chemotherapy)

b. Age, Gender, and Ethnic Background

Males 10-17.99 years old, any ethnic background (identical to our clinical population) were recruited; those over 18 years old at f/u are reconsented,

c. Vulnerable Populations

The study is directed towards children because the purpose of the study is to evaluate growth. We will be monitoring for side effects closely.

d. Rationale for Exclusion of Certain Populations

All boys who fit under our inclusion criteria, regardless of ethnic background, will be included. Girls are excluded as aromatase inhibitor therapy will increase testosterone, causing untoward effects for girls.

e. Stanford Populations

None

f. Healthy Volunteers

None

g. Recruitment Details

The first person identifying patients for recruitment will be physicians in the Pediatric Endocrine Division at Lucile Packard. The protocol director will then continue the recruitment process in more detail.

h. Eligibility Criteria

i. Inclusion Criteria

Outpatient males with: Age 10-17.99 years; re-consented if over 18 years old at follow up Current height less than 5th percentile OR Predicted adult height (based on bone age) more than 10 cm below target height (mid parental height)

- Lab evidence of puberty: serum LH >0.3 IU/L and testosterone >15 ng/dl
- ii. Exclusion Criteria

Bone age xray more than 14 years FSH >20 IU/L

i. Screening Procedures

Pediatric endocrinologists will recruit all patients who qualify based on our inclusion criteria. Qualifying labs and bone age xray are usually obtained as part of routine clinical assessment of boys with short stature and/or delayed puberty, or would be obtained after enrollment and consent.

j. Participation in Multiple Protocols

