7. RISKS

a. Potential Risks

i. Investigational devices

None

ii. Investigational drugs

None

iii. Commercially available drugs, biologics, reagents or chemicals

1) Arthralgia - reported in post-menopausal women at a frequency rate of 20-35%, lower in premenopausal women. Arthralgias have NOT been reported in the pediatric population.

2) Bone health - In adult women, there has been a reported decrease in bone mineral density by 6-7% after 5 years of therapy. We only have short-term data for young boys. Preliminary 1 year data did not show a difference in DEXA- measured bone mineral density in growth hormone (GH) deficient boys using Anastrozole in combination with GH. In boys with idiopathic short stature, there was no statistical difference between the treatment group using Letrozole versus the control group.

3) Fertility - In estrogen receptor knockout male mice, there is a progressive impairment of fertility. In one study using anastrozole in GH deficient boys, there was no difference in sperm parameters.

4) Metabolic parameters: lipids, insulin - In adult men with aromatase deficiency, increased cholesterol and increased insulin resistence has been descibed. In one study using Letrozole in pubertal boys, there was a significant decrease in HDL cholesterol, but all other lipids were unaffected. No changes have been reported in insulin sensitivity.5) Higher than normal testosterone levels could cause hair loss or behavioral changes. Neither has been reported in studies to date.

6) Growth velocity - excessive reduction in growth rate, which seems more likely to occur during the suppression of estrogen levels with Letrozole therapy. Procedures

Blood draws at each visit. Bone age annually. DEXA scan and lateral spine film at baseline and two years into the study. Radioisotopes/radiation-producing machines

DEXA scan which has less radiation than a standard chest XRAY; bone age and lateral spine x-ray. Physical well-being

Routine clinical history. Psychological well-being

Routine clinical history. Economic well-being

None

ix. Social well-being

None

x. Overall evaluation of risk

Medium International Research Risk Procedures

NA

c. Procedures to Minimize Risk

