Randomization to Letrozole vs. Anastrozole in Short Pubertal Males

NCT02137538

June 24, 2021

[name], Principal Investigator [name], Principal Investigator Stanford University Stanford, California 94305

Statistical Methods

Baseline auxologic and hormonal measures were summarized by treatment arm. Laboratory measures over time were presented as means with standard deviation, with key measures (total testosterone, estradiol, IGF-1) additionally displayed as boxplots by arm. Growth velocity (cm/year), height (cm), bone age (months), predicted adult height (cm), and DEXA z-scores over time were similarly visualized. Adverse events were listed by arm, and spinal film was assessed qualitatively.

To include all patients in an intent-to-treat approach, mixed effects linear regression was used to model each outcome as a function of treatment arm, indicators for follow-up timepoints, and their interaction for assessing effect modification of annual change by arm. Within-patient correlation was accounted for by a random effect. Estimated change since baseline with 95% confidence intervals were presented by arm if effect modification was deemed significant at the 0.05 alpha level and as an overall effect otherwise. All analyses were performed in the R statistical computing framework, version 4.0¹.

¹ R Core Team (2020). R: A language and environment for statistical computing. R Foundation for Statistical Computing, Vienna, Austria. URL https://www.R-project.org/

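### Growth velocity appears to be reported as change since baseline, although no pre-treatment velocity is defined or scheduled; a direct between-arm comparison of velocity after the first dose is the safer analysis.

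*SAP*

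**What the plan says.** The SAP (Statistical Methods) names the measures followed over time: "Growth velocity (cm/year), height (cm), bone age (months), predicted adult height (cm), and DEXA z-scores over time were similarly visualized". It then uses mixed-effects linear regression to "model each outcome as a function of treatment arm, indicators for follow-up timepoints, and their interaction", with a random effect for the patient. On reporting, it states that "Estimated change since baseline with 95% confidence intervals were presented by arm if effect modification was deemed significant" at the 0.05 level; otherwise one overall effect is given. The SAP does not say how velocity is computed, over what interval, or which timepoint is its reference. It summarises baseline auxologic measures by arm without listing them.

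The protocol (section 2, Procedures) goes from consent to randomisation and describes no run-in. Eligibility (section 6h) uses height percentile or predicted height, hormone levels and bone age. Screening (section 6i) mentions laboratory tests and bone age. None of these asks for an earlier height. Visits are 6-monthly on treatment and annual afterwards (section 6m).

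Velocity matters to the trial's aims. Section 1 asks whether growth rates differ between the drugs. Section 7a lists as a risk "excessive reduction in growth rate, which seems more likely to occur during the suppression of estrogen levels with Letrozole therapy". Section 2 (Procedure Risks) adds that "the medication may be reduced or discontinued, specifically if growth velocity falls below normal".

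**The concern.** Height, bone age, predicted adult height and the DEXA z-score can each be measured at one visit before the first dose, so change since baseline has a clear meaning for them. Velocity cannot. On scheduled visits alone, the first velocity spans time on drug. If it serves as the reference, the model measures change from one on-drug interval to another, and any effect already present in the first interval is subtracted away.

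The reporting rule adds to this. If the interaction is not significant, the SAP presents one overall change for both arms. The arm main effect, where a constant difference would sit, is not among the estimates it says it presents. The planned velocity output could then read as no difference between drugs on a measure that the protocol itself expects may differ.

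**Working it through.** The documents give no growth-velocity figure, standard deviation, effect size or power, so there is no stated number to reproduce. All growth inputs below are assumptions chosen to show the mechanism.

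**1. Contrast algebra.** Let the drop in velocity in the first on-drug interval be dA (anastrozole) and dL (letrozole), and let a fraction r of each drop be recovered by a later interval.

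- Pre-treatment reference: letrozole minus anastrozole difference in change is -(dL - dA) at the first interval and -(1 - r)(dL - dA) later.
- First on-drug interval as reference: the later change is r·dA and r·dL within the arms, and the difference is r(dL - dA). The amount -(dL - dA) moves into the arm main effect.

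With dA = 0.5 and dL = 1.5 cm/year:

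| Recovery r | Pre-treatment reference: difference at first interval | Pre-treatment reference: difference later | On-drug reference: change A, L | On-drug reference: difference |
|---|---|---|---|---|
| 0 | -1.0 | -1.0 | 0, 0 | 0 |
| 0.5 | -1.0 | -0.5 | +0.25, +0.75 | +0.5 |
| 1 | -1.0 | 0 | +0.5, +1.5 | +1.0 |

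With an on-drug reference, a sustained drop of any size gives a change of 0. If the slowing later recovers, the arm that slowed more appears to gain more. With equal sustained drops of 1 cm/year, the pooled change is 0 instead of -1.

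**2. Simulation of the SAP's model.** Assumptions: 60 boys per arm, pre-treatment mean 6 cm/year, sustained drops of 0.5 and 1.5, between- and within-patient SD 1.2 cm/year each, independent errors, three on-drug intervals, a likelihood-ratio test of the interaction at 0.05, and 150 replicates.

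- Pre-treatment velocity as reference: interaction estimate -1.02 cm/year; significant in 143/150 = 95%.
- First on-drug velocity as reference: interaction estimate -0.01; significant in 4/150 = 3%, which is the nominal 5% within simulation error. The arm main effect is -1.03.

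**3. Direct comparison.** On the same assumptions, one interval has SD √(1.2² + 1.2²) = 1.70 cm/year. A two-sample comparison of a 1.0 cm/year difference has power of about 90% with 60 per arm and 63% with 30. Sixty per arm is half the planned 120. The protocol stopped randomising at its March 2016 renewal, so the randomised number may be smaller.

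**4. Why 12 months.** The measurement-error SD of a velocity is √2 × (height SD) / (interval in years). For an assumed height SD of 0.2, 0.3 or 0.5 cm it is 0.57, 0.85 or 1.41 cm/year over 6 months, and 0.28, 0.42 or 0.71 over 12 months. Doubling the interval halves the error whatever the height SD.

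**The case against.** **A pre-treatment velocity may exist.** Boys come from the centre's own endocrinology practice, and the SAP refers to baseline auxologic measures. A reader might infer that the reference velocity is certainly on drug. The documents neither state nor exclude a velocity from earlier clinic heights, so this stays conditional. If such heights were used, their source and minimum interval are still undefined.

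**Velocity may not be in the model.** It is named only in the sentence on plots, and the modelled outcomes are not listed. Inclusion is the natural reading, since no outcome is exempted, but it is not explicit.

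**The effect can be seen elsewhere.** This is the strongest objection. Height has a true pre-dose value, so its change from baseline to month 12 is the growth over 0-12 months. An arm difference of 1 cm/year sustained for one year appears as about 1 cm in the height model. Velocity is also plotted over time. A reader might infer that the whole effect is lost. It is not: it is lost from the velocity change estimate and its interaction test.

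**Two further inferences fail.** A reader might take the feared slowing to be early, but section 7a ties it to estrogen suppression on letrozole and gives no timing. A reader might also suppose that 6- and 12-month velocities are mixed in one model. The SAP does not give the interval, and its description of the interaction in terms of annual change points, if anything, to yearly intervals.

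**The clinical criterion is separate.** The provision on reducing or stopping drug compares velocity with normal, not with the boy's own baseline. It shows that velocity matters but does not itself depend on the SAP's baseline.

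**Conclusion.** The point holds in conditional form. On scheduled study heights alone, change since baseline for velocity uses an on-drug reference. A sustained arm difference then contributes 0 to the velocity change estimate and to the interaction test, and a difference that recovers contributes with the opposite sign. In the assumed example, the estimated difference in change goes from about -1.0 to about 0 cm/year, and the interaction test from 95% to about 3% significant.

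This rests on velocity being one of the modelled outcomes and on no pre-dose heights having been used. The 1 cm/year difference and the SDs are illustrative. The documents do not support saying that the effect vanishes from the analysis as a whole. The stated endpoint, final height, is untouched. The change is still worth making, because a direct comparison of randomised arms is valid whichever baseline exists and answers the protocol's question about growth rates.

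**What to change.** For growth velocity only, replace change since baseline in the SAP with the following:

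- **Main analysis.** Compare the randomised arms on velocity over 0-12 and 12-24 months from the first dose, computed from heights already measured. Give the between-arm difference and 95% confidence interval for each interval, whether or not the interaction is significant.
- **Sensitivity analysis.** Where pre-dose clinic heights span a minimum interval stated in the SAP, add that pre-dose velocity as a baseline covariate. Keep it out of the main analysis so that boys without it are not dropped, in line with the SAP's aim of including all patients.
- **Definition.** State the source heights and the permitted window around 12 and 24 months.

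The cost is SAP wording, a recalculation from existing heights and a chart search in the centre's own records. No new visit or measurement is needed. The downside is small: fewer and longer velocity intervals, and some overlap with the height model.

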1. PURPOSE OF THE STUDY

a. Brief Summary

The purpose of the study is to determine if there are differences in the final height or hormone profile of patients placed on different forms of aromatase inhibitor now routinely used to increase stature; namely, Anastrozole and Letrozole. It also should determine if there are differences in the side effect profiles of the two drugs to be used. **Objectives**

We hope to learn if there are differences in effects of different forms of aromatase inhibitors on growth. There have been 3 randomized controlled trials using aromatase inhibitors to improve stature in a variety of circumstances (delayed puberty, idiopathic short stature, growth hormone deficiency), but no actual comparative trials between the different forms. We hope to elucidate if there are differences in the growth rates/final heights between the different forms of therapy. This will certainly add to the current, somewhat small literature about the use of these drugs, although they are widely used. We also will look at the differences between the side effect profiles of the two medications. **Rationale for Research in Humans**

Since we are looking at final adult heights, human subjects are necessary.

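### The SAP uses the between-drug difference in change only as a reporting gate, and neither branch specifies that difference with a confidence interval

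*SAP*

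**What the plan says.** The Protocol's Brief Summary (section 1) gives the purpose as to "determine if there are differences in the final height or hormone profile of patients placed on different forms of aromatase inhibitor". Its Objectives add: "We hope to elucidate if there are differences in the growth rates/final heights between the different forms of therapy". The end point in section 2g is: "Our end point is final height which is defined as less than 2 cm of growth per year".

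The SAP's Statistical Methods section is the only analysis plan; the Protocol has no analysis section. It models each outcome on arm, indicators for the follow-up timepoints and "their interaction for assessing effect modification of annual change by arm". It adds that "Within-patient correlation was accounted for by a random effect". The modelled changes from baseline, with 95% CIs, "were presented by arm if effect modification was deemed significant at the 0.05 alpha level and as an overall effect otherwise".

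Some output does not depend on the test. Baseline measures are summarised by arm and adverse events are listed by arm. "Laboratory measures over time were presented as means with standard deviation", without saying whether by arm, while total testosterone, estradiol and IGF-1 also get boxplots by arm. The next sentence covers growth velocity, height, bone age, "predicted adult height (cm), and DEXA z-scores over time were similarly visualized".

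**The concern.** Dropping a non-significant interaction is a familiar simplification when the modifier is a secondary covariate. Here the modifier is the randomised treatment, so dropping the term removes the comparison that the trial exists to make.

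If the rule is followed exactly, each outcome with p of 0.05 or more ends with one pooled change as its modelled result. Both arms receive an aromatase inhibitor and there is no untreated group, so that change mixes drug effect with ordinary pubertal growth. It says nothing about one drug against the other. A reader may take the pooling as evidence of equivalence, although a small trial gives the same result when the drugs differ. When p is below 0.05, the arms are shown separately only because they were found to be far apart, so the displayed gap tends to be too large.

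**Working it through.** The plan gives no power, SD, target difference or number per arm, so there is no stated figure to reproduce. The main check is on the text; the arithmetic only illustrates the consequence.

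**1. What the interaction is.** Take baseline as the reference timepoint and let L = 1 for letrozole, 0 for anastrozole. At follow-up time t the mean is a + bL + g(t) + d(t)L.
- Change on anastrozole: g(t).
- Change on letrozole: g(t) + d(t).
- Letrozole-minus-anastrozole difference in change: d(t), the interaction coefficient.
- The arm coefficient b is the baseline difference, so reporting it would not fill the gap.

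**2. What each branch specifies.**
- p < 0.05: g(t) and g(t) + d(t), each with its own 95% CI. d(t) and its CI are not named.
- p ≥ 0.05: one change averaged over both drugs. d(t) is absent.
- Output that does not depend on p: descriptive summaries and plots, with no estimate or interval for d(t).

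The subject of the reporting sentence is change from baseline, so its pooled branch means a change averaged over arms, not an overall treatment contrast.

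**3. How often a real difference would appear only as a pooled change.** Assumptions: 1:1 allocation, two-sided 0.05, no dropout, a test at one timepoint, and differences in units of the SD of change. I take 60 per arm (all 120 planned boys, Protocol section 6a) and 30 per arm. The smaller case is included because randomisation stopped at the March 2016 renewal (Protocol section 2a) and the number randomised is not given.

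SE = sqrt(2/n): sqrt(2/60) = 0.183 and sqrt(2/30) = 0.258.

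P(pooled only) = 1 − [Φ(d/SE − 1.96) + Φ(−d/SE − 1.96)]

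| True difference | 60 per arm | 30 per arm |
|---|---|---|
| 0.3 SD | 62% | 79% |
| 0.5 SD | 22% | 51% |
| 0.8 SD | 1% | 13% |

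For example, at 0.5 SD and 60 per arm, d/SE = 2.74, Φ(0.78) = 0.782, and 1 − 0.782 = 0.218.

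The SAP does not say whether the test is joint over timepoints. For a joint test over three assumed annual visits with a random intercept (correlation 0.5 between changes), the noncentrality is (n/2)·v′R⁻¹v. That is (n/2)·1.5d² for a constant difference and (n/2)·1.111d² for one growing linearly to d at the third visit. Pooled only means the noncentral chi-square on 3 df falls below 7.815. At 0.5 SD this gives 19–33% at 60 per arm and 51–63% at 30, so the choice of test does not change the conclusion.

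**4. What the interval would show.** Half-width = 1.96 × SE = 0.358 SD at 60 per arm and 0.506 SD at 30. A result just short of significance at 60 per arm has an interval from about 0 to 2 × 0.358 = 0.72 SD. The pooled branch specifies nothing that conveys this.

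**5. Selection when the gate opens.** By simulation of the normal estimate at a true 0.5 SD, the mean estimate among significant results is 0.569 at 60 per arm (0.569/0.5 = 1.14 times the truth) and 0.710 at 30 (1.42 times).

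**The case against.** The strongest reply is that the arms are never really hidden. The growth and DEXA sentence says those outcomes are displayed similarly, directly after boxplots by arm. The natural reading is by-arm boxplots whatever the p-value. That stands: a reader who inferred that a non-significant test removes all sight of the two arms would be going further than the SAP allows. But boxplots give no modelled difference and no interval.

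Second, in the significant branch the arms contain different boys, so a reader can subtract the two changes and combine the standard errors approximately. That also stands, so the non-significant branch is the more serious one.

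Third, the SAP is a two-paragraph summary and nowhere says that interaction coefficients will be withheld. This is fair. One might infer that the difference was suppressed; the documents support only that it is not specified.

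Fourth, it is tempting to say that near-final height lies outside the model. The SAP never lists its timepoints, height is among its outcomes, and boys are followed until growth slows, so this cannot be shown. What can be said is that the SAP does not explain how near-final height, which boys may reach at different times, enters the comparison.

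Finally, the percentages rest on assumed numbers and visit schedules and are not tied to centimetres or hormone units. That is correct, and the textual defect does not need them.

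**Conclusion.** The concern holds, and it needs correcting because the missing contrast is the trial's stated question. This is a written rule that leads to the wrong output, not merely absent detail. Where the interaction is not significant, it puts an uncontrolled pooled change in place of the randomised comparison. Where it is significant, it shows the arms only after selection and still names no interval for their difference. The SAP also leaves open how the stated end point enters the comparison.

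This conclusion rests on the wording of the SAP and the Protocol's purpose. The illustrative sizes depend on assumed allocation, numbers per arm and form of test. They show that missing a moderate difference is plausible, not how often it happened. Nothing here implies that the drugs do or do not differ.

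**What to change.** 1. Delete the conditional reporting rule.
2. For every modelled outcome and timepoint, report the letrozole-minus-anastrozole difference in change from baseline with its 95% CI, and both arm-specific changes, whatever the interaction p-value. Base the contrast on randomised boys.
3. Label any pooled figure as change from baseline in treated boys, not as a drug effect.
4. Add one between-arm estimate with 95% CI for near-final height, and say how it is derived.

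Cost: no new data. The visit-level differences come from the model already specified, refitted only if non-randomised boys were included; near-final height needs one added comparison. The SAP is dated June 2021 and written in the past tense, so completed outputs would have to be re-reported, and some intervals are likely to be visibly wide.

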We will be monitoring for arthralgia with the clinical history every 6 months. We will also collect laboratory data every six months: lipids, insulin levels, as well as estrogen and testosterone, gonadotropin and growth hormone levels. We will perform DEXA scans at baseline and two years into study to assess for decreases in bone density. Access to the labs/scans are all password protected.

d. Study Conclusion

The endpoint is final height. We will terminate when the growth rate has decreased to less than 2 cm per year. Since we will be monitoring clinical and performing physical exams every 6 months, if any of the side effects have been clinically significant, we will treat accordingly and/or terminate the use of the therapy.

e. Data Safety Monitoring Plan (DSMC)

i. Data and/or events subject to review

We will be monitoring, through laboratory evaluation, lipids, insulin sensitivity, gonadotropins, sex steroids, and growth hormone levels. We will monitor for changes in bone density through DEXA scans. Person(s) responsible for Data and Safety Monitoring

Protocol Director Frequency of DSMB meetings

All labs/scans will be monitored as soon as theyhave been received from the reference lab. Specific triggers or stopping rules

Physician's clinical assessment based on laboratory evaluation. DSMB Reporting

As needed

vi. Will the Protocol Director be the only monitoring entity? (Y/N)

Yes

vii. Will a board, committee, or safety monitor be responsible for study monitoring? (Y/N)

No

f. Risks to Special Populations

Short-term studies of aromatase inhibitors in this age group have not shown any significant risks, but there is a theoretical risk of issues with bone density, testicular function, and alterations to lipids/carbohydrate metabolism that is present. We will be monitoring for these risks during the course of the study. The direct benefit is increased ultimate height. We will be discussing these theoretical risks with the family in depth and will be obtaining assent from the subjects themselves. **BENEFITS**

Greater final height for the individual participant and possibly improved treatment options for future patients.

9. **PRIVACY AND CONFIDENTIALITY**

All participant information and specimens are handled in compliance with the Health Insurance Portability and Accountability Act (HIPAA) and privacy policies of Stanford University, Stanford Health Care, and Stanford Children's Health.

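### The SAP does not analyse the protocol's endpoint, final height, and separately specifies no between-arm difference with a confidence interval for any outcome it models

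*SAP*

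**What the plan says.** Protocol section 1a gives the purpose: to "determine if there are differences in the final height or hormone profile of patients" on the two drugs. Growth rates and side effects are further aims. Section 2g fixes the endpoint: "Our end point is final height which is defined as less than 2 cm of growth per year". Section 7d repeats that final height is the endpoint and adds: "We will terminate when the growth rate has decreased to less than 2 cm per year". Section 6m expects this 6-7 years after the start of treatment on average. Section 2a says that from the March 2016 renewal "we will no longer randomize to A vs L but use only A, continuing to collect observational data".

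The SAP is two paragraphs under Statistical Methods, dated June 2021. On growth it says: "Growth velocity (cm/year), height (cm), bone age (months), predicted adult height (cm), and DEXA z-scores over time were similarly visualized". Laboratory measures over time are given as means with standard deviations, and total testosterone, estradiol and IGF-1 are also shown as boxplots by arm. Each outcome is then fitted by a mixed model with treatment arm, "indicators for follow-up timepoints, and their interaction for assessing effect modification of annual change by arm", plus a patient random effect. Estimated change since baseline, with a 95% CI, is "presented by arm if effect modification was deemed significant at the 0.05 alpha level and as an overall effect otherwise". No primary outcome is named.

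**The concern.** A trial randomised between two drugs should produce, for its endpoint, an estimate of the difference between them and a measure of its precision. Followed as written, this SAP does not. Nothing in it is tied to final height or to the 2 cm per year rule. For the outcomes it does model, hormones included, the reader gets either one change pooled over both drugs or two separate within-arm changes.

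A real difference that misses p<0.05 would therefore appear as a single overall effect. Readers could take that as evidence that the drugs are alike, with no model-based interval to tell a small difference from an imprecise one.

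**Working it through.** **Step 1: endpoint against planned outcomes.** The documents give no SD, target difference or power, so there is no figure of the plan's own to reproduce. The first check is textual.

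| Item | Protocol | SAP |
|---|---|---|
| Final height | The endpoint (2g, 7d) | Not named or defined |
| Growth below 2 cm/year | Defines the endpoint | Not used |
| Height over time | Collected at visits | Plotted and modelled by timepoint |
| Predicted adult height | Used for eligibility (6h) | Plotted and modelled by timepoint |

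Each boy reaches final height at his own time, so no single timepoint coefficient for height is the final-height contrast. Predicted adult height is a projection, not the attained value.

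**Step 2: what the model estimates and what is reported.** Write the mean in arm a at time t as μ(a,t). The arm-by-time coefficient at t is

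[μ(L,t) − μ(L,0)] − [μ(A,t) − μ(A,0)],

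which is the between-arm difference in change since baseline. The SAP's two reporting branches are:

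- interaction p<0.05: two within-arm changes, each with a CI;
- otherwise: one change pooled over arms, with a CI.

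The bracketed difference with its CI is in neither branch. Its absence is therefore not caused by the significance rule. The rule does further harm of its own, because it removes even the by-arm model estimates when p≥0.05.

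**Step 3: illustration of the pooling rule.** All of the following are assumptions: equal arms, complete data, baseline plus three annual visits, a random intercept, and height differences of 0, 0.67, 1.33 and 2 cm. SD is that of change from baseline, 3-7 cm, the same at each visit. Planned enrolment of 120 (6a) gives at most 60 per arm, and fewer if boys enrolled after randomisation stopped are counted in it.

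- Residual variance = SD²/2.
- Sum of squared deviations of the four differences about their mean (1 cm) = 1 + 0.111 + 0.111 + 1 = 2.222.
- Noncentrality = (n/2) × 2.222 / (SD²/2). For n = 60 and SD = 5: 30 × 2.222 / 12.5 = 5.33.
- P(pooled) = noncentral F probability below the 5% critical value, with 3 and 3(2n−2) df. For n = 60 that is 3 and 354 df, critical value 2.63, giving 0.538.
- CI half-width for a simple two-arm difference = t × SD × √(2/n). For n = 60 and SD = 5: 1.980 × 5 × 0.1826 = 1.81 cm.

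| n per arm | P(pooled), SD 3 / 5 / 7 | CI half-width (cm), SD 3 / 5 / 7 |
|---|---|---|
| 60 | 0.090 / 0.538 / 0.751 | 1.08 / 1.81 / 2.53 |
| 40 | 0.253 / 0.684 / 0.825 | 1.34 / 2.23 / 3.12 |
| 30 | 0.394 / 0.758 / 0.860 | 1.55 / 2.58 / 3.62 |

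A single-contrast test (two-sided t, noncentrality (2/SD)√(n/2)) gives lower pooling probabilities over SD 3-7: 0.048-0.658 at 60 per arm, 0.162-0.757 at 40 and 0.281-0.807 at 30.

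The result depends heavily on the assumed difference. At n = 60 and SD = 5, P(pooled) is 0.86 for 1 cm, 0.54 for 2 cm, 0.16 for 3 cm and 0.02 for 4 cm.

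**The case against.** The strongest reply is that the SAP is a short methods summary that models every outcome without a closed list, and that height and predicted adult height bear on adult stature. Growth velocity and adverse events by arm also answer stated aims. This stands in part. A reader might infer that the SAP ignores adult stature, or makes no comparison at all, and the documents do not support that. The gap is narrower: the named endpoint is neither defined nor analysed, and the drug difference is not estimated with an interval.

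A reader might also infer that the significance rule is why no between-arm CI exists. Step 2 shows otherwise.

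Nor are readers left with nothing on hormones. Laboratory means and SDs are presented whatever the test shows. If they are by arm, which the text does not say, a rough difference and CI could be worked out from them and the numbers per arm. These remain descriptive summaries. They are not the planned model contrast and do not use the within-patient correlation.

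Pooling after a non-significant interaction can be defended for a subgroup question. Here the interaction is the treatment comparison itself, so that defence does not carry over.

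Finally, a one-value-per-boy analysis of near-final height leaves out boys who have not reached it, whereas the SAP chose mixed models so that all patients are included. That tension is real, and it is why missing boys must be counted and a sensitivity analysis added.

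**Conclusion.** Both defects hold on the text and need correcting. The SAP contains no analysis of final height, and no between-arm difference with a CI for any modelled outcome in either reporting branch.

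Neither conclusion needs an assumed number. The figures in Step 3 concern a year-3 height difference rather than final height. They rest on an assumed 2 cm difference and SD 3-7 cm, and they carry no weight for severity. A reader might take them as showing that the trial will probably hide a real effect. The documents give neither the SD nor the difference needed to say so.

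The documents also do not require that the endpoint height be measured off treatment. Section 7a says an excessive fall in growth rate seems more likely with letrozole, but does not call it temporary. The final-height definition should therefore be taken from the protocol as it stands.

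**What to change.** 1. **Report the comparison.** For every modelled outcome, give the between-arm difference in change since baseline with its 95% CI, whatever the interaction p-value. Do not pool the arms because a test was non-significant. This needs only contrasts from models already specified, so it costs almost nothing.

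2. **Address the endpoint in a dated addendum**, labelled as specified after the June 2021 SAP. Compare near-final height by the protocol's own below-2-cm-per-year definition, as randomised, among boys randomised before the March 2016 change. Adjust for baseline height; baseline bone age is optional. Give the number per arm not yet at final height and a sensitivity analysis for them.

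3. **If too few boys have reached it**, say that final height could not be analysed and limit the conclusions to the outcomes modelled.

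Items 2 and 3 cost an addendum, one regression and possibly more follow-up. At 6-7 years on average, boys randomised just before March 2016 would reach final height around 2022-2023, after the SAP date, and the documents do not say how many have done so. The final-height analysis will be post hoc, may be imprecise and may lack some boys.
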